2.3 Study Rationale

Provide the scientific rationale for the research.

Our SABL is the first ambient lighting intervention that utilizes a smart lighting system to accommodate daylight through windows and maintain the lighting condition, without eliminating the daylighting benefits. This approach is more sustainable and potentially maximizes the effect of the ambient lighting interventions.

This SABL is 'smart' in two aspects. First, designing for ambient lighting environments, compared with simple light boxes, makes adherence easier. Second, the new tunable LED technologies address implementation barriers by providing new auto-controlling of light intensity, distribution,

and spectra in nursing home buildings. The SABL system has a pre-programmed 24-hour control schedule on illuminance settings to mimic the natural bright-dark cycle. It will regularly monitor the lighting level using customized photosensors and automatically adjust the lights to accommodate the daylight effect, minimizing staff burden and maintenance efforts, while maximizing the LI effect. Moreover, we will work closely with the nursing homes and co-design the SABL and implementation protocol and obtain input from stakeholders (e.g., care providers, directors of maintenance, and administrators). This will be a critical foundation to implement the SABL on a larger scale.

Our proposed SABL will provide bright light with illuminance targeted at 400 lux and high CS of 0.3 at the eye level, and dim light \leq 40 lux and low CS \leq 0.1 at night to maintain a bright-dark cycle to regulate activity/rest rhythm, improve sleep, and reduce agitation. This dosage selection is based on the current scientific consensus and research evidence. We will measure the light levels received by each participant using a personal, wearable lighting measure device and will use the actual dosage (lux and CS levels) received by participants to analyze the intervention effect. We design the lighting based on lux and CS levels at the eye level in the sitting position, which is more in line with the surrounding surface reflexivity and the lighting the individuals receive.

SABL is a non-invasive, non-labor-intensive, and promising non-pharmacological intervention for persons with dementia and agitation. This is the first study designing an ambient LI for persons with dementia that incorporates daylight and testing the intervention fidelity and feasibility. Findings will inform intervention design, measures, and implementation protocols for future studies.

3.0 Inclusion and Exclusion Criteria

Create a numbered list below in sections 3.1 and 3.2 of criteria subjects must meet to be eligible for study enrollment (e.g., age, gender, diagnosis, etc.).

Vulnerable Populations:

Indicate specifically whether you will include any of the following vulnerable populations in this research. You MAY NOT include members of these populations as subjects in your research unless you indicate this in your inclusion criteria because specific regulations apply to studies that involve vulnerable populations.

The checklists referenced below outline the determinations to be made by the IRB when reviewing research involving these populations. Review the checklists as these will help to inform your responses throughout the remainder of the protocol.

- **Children** –Review “HRP-416- Checklist - Children”
- **Pregnant Women** – Review “HRP-412- Checklist - Pregnant Women”
- **Cognitively Impaired Adults**- Review “HRP-417- Checklist - Cognitively Impaired Adults”
- **Prisoners**- Review “HRP-415- Checklist - Prisoners”
- **Neonates of uncertain viability or non-viable neonates**- Review “HRP-413- Checklist - Non-Viable Neonates” or “HRP-414- Checklist - Neonates of Uncertain Viability”

[Do not type here]

3.1 Inclusion Criteria

Create a numbered list of the inclusion criteria that define who will be included in your final study sample (e.g., age, gender, condition, etc.).

Aims 1 and 2: Residents

We plan to enroll 20 residents with dementia and agitation from each nursing home (Centre Care and Christ the King Manor). Inclusion criteria are as follows:

1. Age≥55
2. English speaking
3. Nursing home residency ≥3 months
4. Presence of dementia. Dementia will be determined based on 1) dementia diagnosis on medical records, 2) a score of ≤12 on the Brief Interview for Mental State (BIMS) on MDS, and 3) a score of ≤22 on the Montreal Cognitive Assessment (MoCA).
5. Presence of agitation over the past week. Agitation will be determined based on 1) presence of agitation symptoms recorded on the most recent Minimum Dataset (MDS) section E, and 2) a score of >45 on the Cohen-Mansfield Agitation Inventory (CMAI).

Aim 3: Staff and administrators

We will enroll 16 staff/administrators from the two nursing homes (Rehabilitation and Skilled Care at Brookline and Centre Care), including three certified nursing assistants (CNAs), one activity staff, one nurse, one director of nursing, one director of maintenance, and one administrator from each nursing home. For CNAs and nurses, priority given to individuals who provide care for the enrolled residents.

Participants inclusion criteria: 1) age ≥18, 2) English speaking, and 3) employed at the facility for ≥3 months.

3.1.1 Does this research involve collecting data from individuals residing outside of the US?

No

Yes – identify the countries where data collection will take place

[Type protocol text here]

3.2 Exclusion Criteria

Create a numbered list of the exclusion criteria that define who will be excluded in your study.

Aims 1 and 2: Residents

Exclusion criteria are major sleep problems, major mental illness, severe vision impairment, and severe acute or terminal illness.

Major sleep problems refer to severe sleep apnea or severe insomnia that affect individuals' physical function and is documented in medical records. Major mental illness includes mental illness that severely impacts their daily function, including schizophrenia and bipolar disorder. Severe acute illness includes health conditions that result in the needs to be hospitalized or hospice care, or individuals being unconscious, or having life expectancy of less than 6 months. Severe vision impairment refers to "severely impaired vision" based on the Minimum Dataset (MDS) or diagnosis of blindness based on medical records.

Aim 3: Staff and administrators

Age < 18 years old and employed at the facility for < 3 months.

3.3 Early Withdrawal of Subjects

3.3.1 Criteria for removal from study

Insert subject withdrawal criteria (e.g., safety reasons, failure of subject to adhere to protocol requirements, subject consent withdrawal, disease progression, etc.).

Aims 1 and 2: Residents:

Participants who fail to adhere to the protocol, consent to withdrawal, or new diagnosis of health conditions meeting exclusion criteria may be removed from the study.

Aim 3: Staff and administrators

Participants who fail to adhere to protocol requirement or consent withdrawal may be removed from the study.

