3.3.2 Follow-up for withdrawn subjects

Describe when and how to withdraw subjects from the study; the type and timing of the data to be collected for withdrawal of subjects; whether and how subjects are to be replaced; the follow-up for subjects withdrawn from investigational treatment.

We will collect information about reasons for withdrawal upon the timing of withdraw.

Aims 1 and 2: Residents:

If any residents who did not complete the procedures of the study may be replaced with a new participant. We aim to replace the participant with a resident from the same facility, if possible. All the data collected from the participants prior to the withdrawal may be included for analysis. The new participants will go through the entire 13-week study procedures from baseline through post intervention.

Aim 3: Staff and administrators

Aim 3: Any participants who did not complete the study procedures may be replaced with a new staff or administrators with a similar role/position at the facility. All the data collected from the participants prior to the withdrawal may be included for analysis.

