5.6.2.3 Assent of Adults Unable to Consent

Describe the process for assent of the subjects. Indicate whether assent will be required of all, some, or none of the subjects. If some, indicate which subjects will be required to assent and which will not.

If assent will not be obtained from some or all subjects, provide an explanation of why not.

Describe whether assent of the subjects will be documented and the process to document assent. The IRB allows the person obtaining assent to document assent on the consent document and does not routinely require assent documents and does not routinely require subjects to sign assent documents.

Affirmative assent will not be obtained for this study. In my experience, when people with dementia are not capable of providing consent, that usually means that their cognitive function is too impaired to have a good understanding of the research (e.g., purposes and procedures). In that case, they would not be able to provide a meaningful assent either. Thus, in this study, when the residents cannot provide consent, we will not ask for their assent.

Alternatively, when we interact with them and conduct research procedures, such as asking questions for cognitive assessment and putting on the lighting monitor, we will ask their permission and observe their verbal response and non-verbal behavioral cues. When the resident verbally agrees or does not show observable resistance for the monitor. If they express observable verbal or non-verbal resistance to the procedures, such as stating "go away" "I don't want that" or push away the monitor, we will not proceed with the procedures and may approach the resident at a later time.

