7.2.2 Visit 2 or Day 2 or Post-test, etc. (If applicable)

Provide a description of what procedures will be performed on visit 2 or day 2 or post-test in order of how these will be done. If your study involves more than two sessions or visits replicate this section for each additional session or visit (e.g., 7.2.3, 7.2.4, etc.). If your study involves only one session or visit, delete this section.

Aim 1:

Visits 2-6: After the intervention starts, we will measure agitation, BPSD, affect, and sleep, and intervention-related adverse effects using the CMAI, NPI-NH, ARS, PSQI, and adverse effect checklist once every two weeks.

Aim 2:

Visits 2-6: After light is installed, we will monitor the lighting by 1) on-site manual light measurements twice a week for 13 weeks, and 2) a personal light monitor, LYS button, placed on participants, all day, 7 days a week, every two weeks for 13 weeks.

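### Residents may be removed for undefined non-adherence or a newly met exclusion, with no outcome follow-up afterwards, so missing Aim 1 outcomes may be related to response

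*Protocol*

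**What the plan says.** Protocol section 3.3.1 covers residents who "fail to adhere to the protocol, consent to withdrawal, or new diagnosis of health conditions meeting exclusion criteria may be removed from the study". No section says what counts as non-adherence for a resident.

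The exclusion criteria that a new diagnosis could meet are in section 3.2. Two of them could arise within 13 weeks. One is insomnia, in a limited form: "Major sleep problems refer to severe sleep apnea or severe insomnia that affect individuals' physical function and is documented in medical records". The other is acute illness: "Severe acute illness includes health conditions that result in the needs to be hospitalized or hospice care".

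Section 3.3.2 deals with what follows. The only data collection it specifies is this: "We will collect information about reasons for withdrawal upon the timing of withdraw". A non-completer may be replaced by a new resident, who starts again from baseline. On data already in hand it says: "All the data collected from the participants prior to the withdrawal may be included for analysis".

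For the follow-up visits, section 7.2.2 says "we will measure agitation, BPSD, affect, and sleep, and intervention-related adverse effects using the CMAI, NPI-NH, ARS, PSQI" and an adverse-effect checklist, every two weeks. Sections 7.2 and 7.2.1 and Table 2 take these ratings from staff caregivers. Section 8.3 and the SAP (Aim 1) analyse baseline to post-intervention change in CMAI, NPI-NH and ARS, with average light dose from the personal monitor as the independent variable. Neither document defines an analysis set, a rule for missing outcomes, or assessment after removal.

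**The concern.** Two of the three grounds for removal can be touched by the outcomes. Section 1.2 places agitation, sleep and side effects among the primary outcomes, and a new diagnosis of severe insomnia is a ground for removal. Section 2.1 counts wandering and resisting as agitation. Taking part here means wearing a monitor and being guided to designated areas, so the behaviour under study could be read as non-adherence. Section 10.0 names increased agitation as a rare possible risk of the light.

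If removal depends on how a resident responds, the change scores that remain are a selected sample. In a crossover the loss is larger than one score, because the resident's own comparison between conditions can go too, and section 7.1 gives that comparison as the reason for the design. A replacement restores the head count but not the missing outcome.

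**Working it through.** **1. Follow a removed resident through Table 1.** Ratings fall in weeks 1, 3, 5, 7, 9, 11 and 13. The first condition runs in weeks 2 to 5, washout in 6 to 7, the second condition in 8 to 11, and the final phase in 12 to 13.

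- Home A (SABL first), removed in week 4: ratings exist for weeks 1 and 3. There is no post-intervention rating and none under control.
- Home B (SABL second), removed in week 10: ratings exist up to week 9. There is no post-intervention rating.

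In both cases the planned Aim 1 change score cannot be formed. Section 3.3.2 does not require the existing ratings to be used or later ones to be collected.

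**2. The plan's own figures (section 8.2).** Inputs: 40 enrolled, 10% attrition, d = 0.53, alpha 0.05, power 0.92. Attrition: 40 × 0.90 = 36, as stated. For power I used a paired t-test on within-person change, with noncentrality d√n: 0.53 × √36 = 3.18 and 0.53 × √40 = 3.35.

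| n | two-sided, t (normal) | one-sided, t (normal) |
|---|---|---|
| 36 | 0.871 (0.889) | 0.930 (0.938) |
| 40 | 0.905 (0.918) | 0.950 (0.956) |

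The stated 0.92 is close to one-sided at 36 or two-sided at 40, but not to two-sided at 36. The sidedness is not given. Clustering by home is ignored because no intraclass correlation is stated.

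**3. What selective removal could do (illustration).** Assumptions: true effect zero, normal change scores, a fraction p removed, and a correlation ρ between the tendency to be removed and worsening on SABL. The shift in the remaining mean towards SABL is

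shift = ρ × φ(z) / (1 − p), where z is the 1 − p normal quantile.

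For p = 4/40 = 0.10, z = 1.282 and φ(z) = 0.1755, so φ(z)/(1 − p) = 0.195. Hence 0.3 × 0.195 = 0.058 SD and 0.5 × 0.195 = 0.097 SD. A simulation with 40 residents (100,000 runs, two-sided paired t at 0.05 on those left) gave:

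| Removed | ρ | Shift towards SABL (SD) | Type I error |
|---|---|---|---|
| 4 | 0 | none | 0.051 |
| 4 | 0.3 | 0.057 | 0.064 |
| 4 | 0.5 | 0.095 | 0.094 |
| 4 | 1 | 0.188 | 0.276 |
| 2 | 0.3 to 0.5 | 0.031 to 0.052 | 0.054 to 0.065 |
| 6 | 0.3 to 0.5 | 0.080 to 0.133 | 0.077 to 0.132 |

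The documents give no value for ρ. By symmetry, a ρ of opposite sign gives the same shift against SABL.

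**4. With outcomes on all 40.** Selection through removal disappears, and two-sided power in the table under step 2 is 0.905 rather than 0.871.

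**The case against.** The grounds are narrower than they look. Removal is discretionary. Insomnia counts only as a new, severe, charted diagnosis that impairs physical function, so a poor PSQI score triggers nothing. Worsened agitation is not itself a ground. Sleep is not among the outcomes that section 8.3 and the SAP analyse for Aim 1, so a sleep-based removal affects the analysed outcomes only if it goes with worse CMAI, NPI-NH or ARS.

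The rest of the Protocol leans towards accommodation. Residents are encouraged, not required, to use designated areas (section 7.1). For those who "push away the monitor, we will not proceed with the procedures and may approach the resident at a later time", section 5.6.2.3 means a pause in one procedure. That does not contradict section 3.3.1, although nothing says where repeated refusal becomes non-adherence.

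A reader might infer that those who do worst on SABL are removed by rule and that the effect is therefore inflated. For instance, if all 4 expected attriters would have worsened by 0.5 SD while the other 36 improve by 0.53 SD, the true mean is (36 × (−0.53) + 4 × 0.5)/40 = −0.427, and reporting −0.53 overstates it by 24%. The documents do not support this reading. The 10% is general attrition from similar populations, and the exclusions also cover hospital, hospice and terminal illness. The monitor is worn in control and washout weeks too, and a mock installation precedes control (section 7.4.25), so refusal can occur in any period. Only aversion to the light itself is specific to SABL. If SABL does calm residents, agitation-driven removals would gather under usual light and bias against it.

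Nor do the documents show that harm would be hidden. Withdrawal reasons are collected, events believed related to the lighting are followed until resolved or stable (section 18.2), and the checklist covers worsened behavioural symptoms (section 19.1.2).

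A multilevel model on all available visits could also reduce bias if data were missing at random. The plan commits to neither that model nor that assumption.

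These points remove any claim about direction or size. They leave the structural gap in place: undefined discretion to remove, no outcome afterwards, and optional use of earlier data.

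**Conclusion.** The concern holds in a limited form. Followed as written, sections 3.3.1 and 3.3.2 with the Aim 1 analysis allow outcomes to be lost for reasons that may be related to response, and nothing in either document corrects for this.

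The direction and size of any bias are unknown. There is none if removal is unrelated to response. Under a true null, with 4 of 40 removed and a correlation of 0.3 to 0.5 with worsening on SABL, the shift is about 0.06 to 0.10 SD towards SABL, with type I error of 0.064 to 0.094. Those figures assume that all the expected attrition is selective to that degree, and they use a simple paired test instead of the planned dose model. They show scale and do not predict the trial's result. The change is worth making because the ratings that would close the gap are already scheduled.

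**What to change.** In sections 3.3.1 and 3.3.2, separate stopping the light or the monitor from stopping observation. Whether a resident stays under the light is a clinical decision that this change leaves alone. Then state the following:

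- Unless consent is withdrawn, and as far as circumstances allow (for example, while the resident remains in the home), residents who do not adhere, refuse the monitor or newly meet an exclusion criterion continue the two-weekly staff-rated assessments (CMAI, NPI-NH, ARS, sleep, adverse effects) through week 13.
- Data collected before withdrawal *will* be included, in place of *may*.
- All enrolled residents are analysed in their home's randomised sequence, and removed residents stay in the analysis even if replaced.
- The lighting condition at the time is recorded with the reason for withdrawal.
- An analysis by assigned condition (SABL or usual light) is added to section 8.3 and the SAP. The dose-based model cannot use a resident without monitor data, so continued ratings alone would not bring that resident into Aim 1.

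The cost is protocol, SAP and consent wording. The ratings need no resident cooperation and would have been due had the resident stayed. At the 15 dollars per assessment in section 13.0, four residents followed for all six follow-up visits come to at most 4 × 6 × 15 = 360 dollars. The downside is slight dilution of the effect by non-adherent residents. Some ratings will still be missing, for example during a hospital stay.

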3.3.2 Follow-up for withdrawn subjects

Describe when and how to withdraw subjects from the study; the type and timing of the data to be collected for withdrawal of subjects; whether and how subjects are to be replaced; the follow-up for subjects withdrawn from investigational treatment.

We will collect information about reasons for withdrawal upon the timing of withdraw.

Aims 1 and 2: Residents:

If any residents who did not complete the procedures of the study may be replaced with a new participant. We aim to replace the participant with a resident from the same facility, if possible. All the data collected from the participants prior to the withdrawal may be included for analysis. The new participants will go through the entire 13-week study procedures from baseline through post intervention.

Aim 3: Staff and administrators

Aim 3: Any participants who did not complete the study procedures may be replaced with a new staff or administrators with a similar role/position at the facility. All the data collected from the participants prior to the withdrawal may be included for analysis.

4.0 Recruitment Methods

- Upload recruitment materials for your study in CATS IRB (<http://irb.psu.edu>). DO NOT include the actual recruitment wording in this protocol.
- StudyFinder: If StudyFinder (<http://studyfinder.psu.edu>) is to be used for recruitment purposes, separate recruitment documents do not need to be uploaded in CATS IRB. The necessary information will be captured from the StudyFinder page in your CATS IRB study.
- Any eligibility screening questions (verbal/phone scripts, email, etc.) used when contacting potential participants must be uploaded to your study in CATS IRB (<http://irb.psu.edu>).

[Do not type here]

4.1 Identification of subjects

Describe the source of subjects and the methods that will be used to identify potential subjects (e.g., organizational listservs, established recruitment databases, subject pools, medical or school records, interactions during a clinic visit, etc.). If not recruiting subjects directly (e.g., database query for eligible records or samples) state what will be queried, how and by whom.

StudyFinder:

- If you intend to use StudyFinder (<http://studyfinder.psu.edu>) for recruitment purposes, include this method in this section.
- Information provided in this protocol, including the description of study procedures, compensation, and recruitment, needs to be consistent with information provided on the StudyFinder page in your CATS IRB study.

For Penn State Health submissions using Enterprise Information Management (EIM) for recruitment, and for non-Hershey locations as applicable, attach your EIM Design Specification form in CATS IRB (<http://irb.psu.edu>). See “HRP-103- Investigator Manual, Study Recruitment” for additional information. DO NOT include the actual recruitment material or wording in this protocol.

Aims 1 and 2: Residents

We will conduct this study from local nursing home facilities.

We will ask nursing home administrative staff at each facility to help identify potentially eligible residents who meet our broad inclusion criteria: 1) age ≥ 55 , 2) English speaking, 3) long-term stay at the facility for at least 3 months, and 4) diagnosis of dementia.

The eligibility of the potential participants identified by nursing home staff will be confirmed by the research team after consent. The research team will review the residents' medical records for inclusion and exclusion criteria (age ≥ 55 , English speaking, nursing homes residency ≥ 3 months, presence of dementia, and presence of agitation over the past week) and collect information on resident's cognitive function and agitation through the proxy report of their primary caregivers (CNA or nurse) to confirm eligibility. Eligible participants will be approached for consent once their contact information is obtain

Aim 3: Staff and administrators

We will ask nursing home administrative staff to help identify potentially eligible staff/administrators for the criteria of interest: age ≥ 18 , English speaking, employed for ≥ 3 months, and in the position of interest at the facilities. Their eligibility will be verified by the research team.

4.2

Recruitment process

Describe how potential subjects first learn about this research opportunity or indicate 'not applicable' if subjects will not be prospectively recruited to participate in the research. Subject recruitment can involve various methods (e.g., approaching potential subjects in person, contacting potential subjects via email, letters, telephone, ResearchMatch, or advertising to a general public via flyers, websites, StudyFinder, newspaper, television, and radio etc.). DO NOT include the actual recruitment material or wording in this protocol.

[Do not type here]

4.2.1 How potential subjects will be recruited.

Aims 1 and 2: Residents

Referral of nursing staff. Once the potentially eligible residents are identified, recruitment will be conducted in a few ways.

First, the nursing home staff will send out a resident recruitment letter (see document attached) to the family/legally authorized representative of the potentially eligible residents. The letter includes the information about a brief

overview of the study and the research team's contact information. The letter also asks the family/LAR to contact the research team if they are interested in letting the residents to participating in the study.

Next, the research team will hold one or more recruitment meetings in person and/or virtually to meet with family, provide an overview about the study, and answer any questions they may have. The research team will ask the family/LAR to provide their contact information, if they are interested in letting the residents to participate in the study or discussing the research further. The Study Overview Slides for the recruitment meetings are attached.

Finally, the research team will post recruitment flyers (see attachment) at the facility and invite family/LAR to contact the research team or leave contact information for the research team to contact them.

Aim 3: Staff and administrators

Flyers will be created and posted in the facility to recruit staff. The research team will hold one or more recruitment meetings at the facility to introduce the study, answer questions, and recruit staff participants. The Study Overview Slides for the recruitment meetings are attached.

4.2.2 Where potential subjects will be recruited.

We plan to recruit participants from local nursing homes. The potential nursing homes we plan to recruit are 1) Centre Care and 2) Christ the King Manor.

4.2.3 When potential subjects will be recruited.

Participants will be recruited as soon as we have IRB approval and permission from nursing homes.

4.2.4 Describe the eligibility screening process. Screening begins when the investigator obtains information about or from a prospective participant in order to determine their eligibility.

- Eligibility screening is occurring *before* consent* - describe the process below
- Eligibility screening is occurring *after* consent - describe the process below
- Eligibility screening is occurring, consent is not being obtained in this research - describe the process below
- Not applicable - Eligibility screening is not being done in this research

Aims 1 and 2: Residents

The screening process for residents involves three steps: 1) initial screening conducted by nursing home staff, 2) chart reviews conducted by the research team, and 3) interviews with primary staff/caregivers conducted by the research team. The step 1 screening will be conducted prior to the consent, and the steps 2 and 3 will be conducted after consent.

For step 1, the nursing home staff will conduct an initial screening based on our broad inclusion criteria: 1) age ≥ 55 , 2) English speaking, 3) long-term stay at the facility for at least 3 months, and 4) diagnosis of dementia.

For step 2, after the informed consent is obtained from LAR or resident as appropriate, the research team will review the residents' medical records to verify their eligibility based on the inclusion and exclusion criteria.

If the resident is not capable to consent and does not have a LAR to provide consent, they will not be eligible to participate in the study.

For residents who pass the step 2 screening, the research team will proceed with the screening and conduct additional assessments to confirm the presence of dementia and agitation. Specifically, the research team will assess residents' cognitive function by interviewing the residents and assess the residents' agitation symptoms based on inputs from the primary staff caregivers, which includes but is not limited to certified nurse assistants (CNAs), licensed practical nurses (LPNs), and registered nurse (RNs).

We will assess residents' cognitive impairment using the Montreal Cognitive Assessment (MoCA). A score of ≤ 22 on the Montreal Cognitive Assessment (MoCA) is considered cognitive impairment and eligible for this research study. We will assess residents' agitation symptoms using the Cohen-Mansfield Agitation Inventory (CMAI), based on the residents' behaviors over the past week. A CMAI score of ≥ 45 is considered presence of agitation and is eligible for this study. Residents who have cognitive impairment (MoCA score ≤ 22) and agitation (CMAI score ≥ 45) are considered eligible and will be enrolled for the study.

Aim 3: Staff and administrators

The screening for staff and administrators will be conducted after consent has been provided. Our inclusion criteria are as below: a) nursing home employed healthcare workers employed for ≥ 3 months, b) age ≥ 18 , and c) English speaking. We will provide the inclusion criteria to the staff during the recruitment meeting and, if they are potentially eligible and interested in participating, the research team will ask them to provide their contact information. Next the research team will reach out to them individually to obtain consent.

In some studies, these procedures may not take place unless HIPAA Authorization is obtained OR a waiver of HIPAA Authorization when applicable for the screening procedures is approved by the IRB.

*Unless informed consent is waived by the IRB, screening before consent is only permitted when screening activities are limited to the collection of information through oral or written communication OR when identifiable private information or identifiable biospecimens is obtained by accessing records or stored identifiable biospecimens. Screening before consent is not permitted if data will be used for activities other than eligibility screening/recruitment (e.g., data analysis).

